**Subgroup Analyses for Efficacy Endpoints**

Efficacy Endpoint	Subgroup			
	Gender	Anhedonia Severity (SHAPS)		Baseline HAM-A (<20, >=20)
		(<=4, >4)	(<=7, >7)	
MADRS total score	X	X	X	X
PRT			X	
EEfRT			X	

**16. SAFETY OUTCOMES**

All outputs for safety outcomes will be based on the Safety Analysis Set.

There will be no statistical comparisons between the treatment groups for safety data, unless otherwise specified with the relevant section.

**16.1. ADVERSE EVENTS**

Adverse Events (AEs) will be coded using Medical Dictionary for Regulatory Activities (MedDRA) central coding dictionary, Version 20.0.

Treatment emergent adverse events (TEAEs) are defined as AEs that started or worsened in severity on or after the first dose of study medication.

See [APPENDIX 2](#) for handling of partial dates for AEs. In the case where it is not possible to define an AE as treatment emergent or not, the AE will be classified by the worst case; i.e. treatment emergent.

An overall summary of number of patients within each of the categories described in the sub-section below will be provided as specified in the templates.

Listings will include TEAEs and Non-TEAEs.

**16.1.1. ALL TEAEs**

Incidence of TEAEs will be presented by System Organ Class (SOC) and Preferred Term (PT) and also broken down further by maximum severity and relationship to study medication.

**16.1.1.1. Severity**

Severity is classed as mild/ moderate/ severe (increasing severity). TEAEs starting after the first dose of study medication with a missing severity will be classified as severe. If a patient reports a TEAE more

Document: C:\Users\q718413\Documents\NEP-MDD-201\_SAP\_v1.0\_Final\_06Dec2018.docx  
 Author: [name]  
 Version Number: 1.0  
 Version Date: 06Dec2018

Template No: CS\_TP\_BS016 Revision 4  
 Effective Date: 01Apr2016  
 Reference: CS\_WI\_BS005

Analysis Plan

---

than once within that SOC/ PT, the AE with the worst case severity will be used in the corresponding severity summaries.

**16.1.1.2. Relationship to Study Medication**

Relationship, as indicated by the Investigator, is classed as "not related", "unlikely related", "possibly related", and "related" (increasing severity of relationship). A "related" TEAE is defined as a TEAE with a relationship to study medication as "possibly related" or "related" to study medication. TEAEs with a missing relationship to study medication will be regarded as related to study medication. If a patient reports the same AE more than once within that SOC/ PT, the AE with the worst case relationship to study medication will be used in the corresponding relationship summaries.

**16.1.2. TEAEs LEADING TO DISCONTINUATION OF STUDY MEDICATION**

TEAEs leading to permanent discontinuation of study medication will be identified from the Adverse Event eCRF page where the action taken with the study treatment was selected as "Drug withdrawn".

For TEAEs leading to discontinuation of study medication, summaries of incidence rates (frequencies and percentages) by SOC and PT will be prepared.

**16.1.3. TEAE'S LEADING TO EARLY STUDY DISCONTINUATION**

TEAEs leading to early study discontinuation will be identified from the relevant question in the Adverse Event eCRF page.

For TEAEs leading to early study discontinuation, summaries of incidence rates (frequencies and percentages) by SOC and PT will be prepared.

**16.1.4. SERIOUS ADVERSE EVENTS**

Serious adverse events (SAEs) are those events recorded as "Serious" on the Adverse Events page of the eCRF. A summary of serious TEAEs by SOC and PT will be prepared.

**16.1.5. ADVERSE EVENTS ASSOCIATED WITH SELF-HARM EPISODES**

TEAEs associated with self-harm episodes will be identified from the relevant question in the Adverse Event eCRF page.

For TEAEs associated with self-harm episodes, summaries of incidence rates (frequencies and percentages) by SOC and PT will be prepared.

**16.2. DEATHS**

If any patients die during the study, as recorded on the "death details" page of the eCRF , the

---

Document:	C:\Users\q718413\Documents\NEP-MDD-201_SAP_v1.0_Final_06Dec2018.docx		
Author:	[name]	Version Number:	1.0
		Version Date:	06Dec2018

Template No: CS\_TP\_BS016 Revision 4  
Effective Date: 01Apr2016

Reference: CS\_WI\_BS005

Copyright © 2009, 2010, 2012, 2016 Quintiles Transnational Corp. All rights reserved.  
The contents of this document are confidential and proprietary to Quintiles Transnational Corp. Unauthorized use, disclosure or reproduction is strictly prohibited.

information will be presented in a data listing.

## 16.3. LABORATORY EVALUATIONS

Results from the central laboratory will be included in the reporting of this study for Hematology, Clinical Chemistry (including Amylase and total Lipase) and Urinalysis. A list of laboratory assessments to be included in the outputs is included in the protocol, [Section 11.4](#).

Presentations will use SI Units.

Quantitative laboratory measurements reported as “< X”, i.e. below the lower limit of quantification, or “> X”, i.e. above the upper limit of quantification, will be converted to X/2 or X respectively for the purpose of quantitative summaries, but will be presented as recorded, i.e. as “< X” or “> X” in the listings, where X has been converted into the SI unit.

The following summaries will be provided for laboratory data:

- Summary tables of actual and change from baseline by visit (for quantitative measurements)
- Shift from baseline to each post-baseline assessment according to normal range criteria (for quantitative measurements and categorical measurements)
- Listing of patients meeting abnormal criteria

Laboratory tests related to patient screening, such as, urine drug screening, hepatitis screening and thyroid function, if available, will be listed only. Results from serum and urine Pregnancy tests will be listed.

### 16.3.1. LABORATORY REFERENCE RANGES AND ABNORMAL CRITERIA

Quantitative laboratory measurements will be compared with the relevant laboratory reference ranges in SI units and categorized as:

- Low: Below the lower limit of the laboratory reference range.
- Normal: Within the laboratory reference range (upper and lower limit included).
- High: Above the upper limit of the laboratory reference range.

## 16.4. ECG EVALUATIONS

Results from the central ECG (Electrocardiogram) Reading Centre will be included in the reporting of this study.

The following ECG parameters will be reported for this study:

- PR Interval (msec)
- RR Interval (msec)

---

Document:	C:\Users\q718413\Documents\NEP-MDD-201_SAP_v1.0_Final_06Dec2018.docx	Version Number:	1.0
Author:	[name]	Version Date:	06Dec2018

Template No: CS\_TP\_BS016 Revision 4  
Effective Date: 01Apr2016

Reference: CS\_WI\_BS005

## Analysis Plan

---

- QRS Duration (msec)
- QT Interval (msec)
- QTcF Interval (msec)
- QTcB Interval (msec)
- Heart Rate (bpm)
- Axis and Voltage (deg)
- Overall assessment of ECG (Investigator's judgment):
  - Normal
  - Abnormal, Not Clinically Significant (ANCS)
  - Abnormal, Clinically Significant (ACS)

Summary tables and boxplots of actual and change from baseline results for all quantitative ECG parameters will be presented.

### 16.4.1. ECG MARKEDLY ABNORMAL CRITERIA

Markedly abnormal quantitative ECG measurements will be identified in accordance with the following predefined markedly abnormal criteria:

- Absolute values for QT interval, QTc interval, QTcB interval and QTcF will be classified as:
  - > 450 msec
  - > 480 msec
  - > 500 msec
- Change from Baseline for QT interval, QTc interval, QTcB interval and QTcF will be classified as:
  - >30 msec increase from baseline
  - >60 msec increase from baseline

Results which meet the above criteria will be flagged in the listing.

## 16.5. VITAL SIGNS

The following Vital Signs measurements will be reported for this study:

- Standing/ Supine Systolic Blood Pressure (mmHg)
- Standing/ Supine Diastolic Blood Pressure (mmHg)
- Standing/ Supine Pulse Rate (bpm)
- Respiratory Rate (breaths/min)
- Temperature (°C)

---

Document:	C:\Users\q718413\Documents\NEP-MDD-201_SAP_v1.0_Final_06Dec2018.docx	Version Number:	1.0
Author:	[name]	Version Date:	06Dec2018

Template No: CS\_TP\_BS016 Revision 4  
Effective Date: 01Apr2016

Reference: CS\_WI\_BS005

Copyright © 2009, 2010, 2012, 2016 Quintiles Transnational Corp. All rights reserved.  
The contents of this document are confidential and proprietary to Quintiles Transnational Corp. Unauthorized use, disclosure or reproduction is strictly prohibited.

Analysis Plan

- Weight (kg)
- BMI (kg/m^2)

Summary tables and boxplots of actual and change from baseline results for all quantitative ECG parameters will be presented.

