would result in receptor occupancy (RO) above 80% for 24-hours in at least 75% of patients at steady state. There were no deaths or SAEs with BTRX-246040 administration in either study. In study NOAC, the most common TEAEs that occurred more frequently with BTRX-246040 than placebo were nausea (7/69 [10.1%] vs. 1/65 [1.5%] patients), insomnia (7/69 [10.1%] vs. 0/65 patients) and dizziness (5/69 [7.2%] vs. 0/65 patients). In study NOAD, the frequency of TEAEs reported was similar between the BTRX-246040 and placebo treatment groups. In both studies, most TEAEs were mild or moderate in severity. There were no notable treatment-related clinical laboratory findings or abnormal ECGs. Vital signs were generally within normal range, with no notable treatment-related changes reported following 40 mg QD BTRX-246040. In Study NOAC, no increase in suicidal ideation or behavior relative to placebo was detected following BTRX-246040 administration, as assessed by the C-SSRS. In Study NOAD, there was no suicidal ideation or behavior following BTRX-246040 administration, as assessed by the C-SSRS. In general, the observed BTRX-246040 concentration time data in patients with MDD were in a similar range to the concentrations observed in the healthy subject study (Study I5J-MC-NOAA [NOAA]) when the data were compared after normalizing for administered dose.

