#### 13.2.11 SAFETY ANALYSES

Safety assessments include AEs, SAEs, vital signs, weight and BMI, laboratory values, neurological exams, C-SSRS, SHSF, SHFU, and ECGs. All safety analyses will be performed on the Safety Analysis Set unless otherwise specified.

The safety/tolerability of BTRX-246040 and placebo will be compared for rates of spontaneously reported TEAEs, SAEs, AEs associated with self-harm episodes, early study discontinuations, discontinuations from BTRX-246040 or placebo, and AEs leading to discontinuation from the study or from BTRX-246040 or placebo.

Data will be pooled from all investigative sites for the analyses.

Safety results will be summarized by treatment. For categorical variables, frequencies and percentages will be reported and for continuous endpoints by visit and change from baseline summaries will be presented.

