**16.5.1. VITAL SIGNS ABNORMAL CRITERIA**

Abnormal quantitative vital signs measurements will be identified in accordance with the following predefined abnormal criteria:

Variable	Unit	Low	High
SBP	mmHg	$\leq 90$ mmHg OR change from baseline $\leq -20$ mmHg OR difference between supine and standing (standing – supine) $\leq -20$ mmHg	$\geq 160$ mmHg OR change from baseline $\geq 20$ mmHg OR difference between supine and standing (standing – supine) $\geq 20$ mmHg
DBP	mmHg	$\leq 50$ mmHg OR change from $\leq -10$ mmHg OR difference between supine and standing (standing – supine) $\leq -10$ mmHg	$\geq 100$ mmHg OR change from baseline $\geq 10$ mmHg OR difference between supine and standing (standing – supine) $\geq 10$ mmHg
Pulse rate	Bpm	$\leq 50$ bpm OR change from baseline $\leq -15$ bpm OR difference between supine and standing (standing – supine) $\leq -15$ mmHg	$\geq 120$ bpm OR change from baseline $\geq 15$ bpm OR difference between supine and standing (standing – supine) $\geq 15$ mmHg
Body temperature	°C	NA	$\geq 38.3$ °C OR change from baseline $\geq 1.1$ °C
Weight	Kg	percentage change from baseline $\leq -7.0$ %	percentage change from baseline $\geq 7.0$ %

Results which meet the above criteria will be flagged in the listing.

Document: C:\Users\q718413\Documents\NEP-MDD-201\_SAP\_v1.0\_Final\_06Dec2018.docx  
 Author: [name]  
 Version Number: 1.0  
 Version Date: 06Dec2018

Template No: CS\_TP\_BS016 Revision 4  
 Effective Date: 01Apr2016  
 Reference: CS\_WI\_BS005

Copyright © 2009, 2010, 2012, 2016 Quintiles Transnational Corp. All rights reserved.  
 The contents of this document are confidential and proprietary to Quintiles Transnational Corp. Unauthorized use, disclosure or reproduction is strictly prohibited.

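### SAP 16.5 (Vital Signs) specifies summaries of ECG parameters instead of vital signs, and no by-arm summary of the standing-minus-supine difference is planned even once that wording is corrected

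*SAP*

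**What the plan says.** SAP 16.5 opens with "The following Vital Signs measurements will be reported for this study" and lists systolic pressure, diastolic pressure and pulse (each standing and supine), respiratory rate, temperature, weight and BMI. Its one sentence on tables and figures is "Summary tables and boxplots of actual and change from baseline results for all quantitative ECG parameters will be presented". SAP 16.4, on ECGs, contains the same sentence.

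SAP 16.5.1 sets limits for abnormal values. For systolic pressure, diastolic pressure and pulse, each Low and High limit joins three alternatives by OR: an absolute level, a change from baseline, and the "difference between supine and standing (standing – supine", in that order). The only output attached to these limits is "Results which meet the above criteria will be flagged in the listing".

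Protocol 13.2.11 says "Safety assessments include AEs, SAEs, vital signs, weight and BMI, laboratory values, neurological exams, C-SSRS, SHSF, SHFU, and ECGs". It adds "Safety results will be summarized by treatment" and, on the form of the summaries, "for continuous endpoints by visit and change from baseline summaries will be presented".

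Three other SAP sections bear on the point. Section 3.3 declares no departure from the protocol. Section 4.3 ties the final analysis to the analyses identified in the SAP. Section 8 refers the format and content of tables to shell templates, which are not among the documents reviewed.

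**The concern.** The SAP is the working instruction for the programming team. Followed literally, 16.5 asks for the ECG tables a second time and for no vital-signs table, although the protocol treats vital signs, weight and BMI as safety assessments to be summarised by arm. Safety and tolerability is a secondary objective of this trial.

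The postural difference is a separate omission. Protocol Table 1 has supine and standing blood pressure and pulse taken at every visit, and the SAP already sets thresholds for the difference. Yet the plan asks for no mean, spread, change or patient count of that difference in either arm.

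The background gives ordinary reasons to want these tables. In the earlier MDD study, dizziness was among the most common events reported more often on drug (5 of 69 against 0 of 65 patients). Reduced body weight is a stated preclinical effect. The present trial escalates to 80 mg, for which the protocol says no PK data exist; it anticipates a mean Cmax of about 350 ng/mL, against 127 ng/mL observed at 40 mg.

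**Working it through.** The plan states no figure to reproduce. The check is a comparison of text, plus a count.

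**1. What each SAP safety section specifies after baseline**

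| SAP section | Measures | Tables or plots specified |
|---|---|---|
| 16.3 Laboratory | Haematology, chemistry, urinalysis | Actual values and change by visit; shifts; listing of abnormal values |
| 16.4 ECG | Intervals, heart rate, axis | Tables and boxplots of ECG parameters |
| 16.5 Vital signs | Blood pressure, pulse, respiration, temperature, weight, BMI | Tables and boxplots of ECG parameters |
| 16.5.1 Abnormal vital signs | Limits, including postural difference | Listing flag only |

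The third row is the defect: the measures are vital signs and the specified output is for ECGs. No other SAP sentence specifies a post-baseline vital-signs table. SAP 10 tabulates weight and BMI by arm, but only at baseline.

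**2. Count of measures affected**

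- Three readings (systolic pressure, diastolic pressure, pulse) × 2 positions = 6.
- Respiratory rate, temperature, weight and BMI = 4.
- Total: 6 + 4 = 10 measures.
- Post-baseline visits with these assessments in Protocol Table 1: Visits 3 to 8 = 6.
- 10 × 6 = 60 measure-by-visit summaries per arm that Protocol 13.2.11 calls for and SAP 16.5 does not specify.

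**3. Does correcting the wording also cover postural change?**

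No. The standing-minus-supine difference is not in the 16.5 list, so a corrected sentence would summarise the supine and standing readings separately. For each patient, let D = standing − supine.

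- Mean(D) = mean(standing) − mean(supine), provided the same patients contribute both readings.
- Var(D) = Var(standing) + Var(supine) − 2 Cov(standing, supine).

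The two separate tables give the first line but not the second, because the covariance is not reported. Nor do they give the number of patients per arm whose D crosses a threshold.

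**4. Does the listing flag fill the gap?**

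Only in part. Because the three alternatives are joined by OR, a Low or High flag does not by itself show whether posture, absolute level or change from baseline triggered it. The SAP asks for no count of flags by arm.

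**The case against.** The strongest reply is that this is a copying slip whose intent is clear. Read literally, the sentence in 16.5 only repeats 16.4, and it stands under a list of vital signs that are to be reported. Protocol 13.2.11 already commits to summaries by treatment, by visit and as change from baseline, and SAP 3.3 leaves that commitment in force. SAP 6.4 provides visit windows for safety variables assessed at each visit. The shells may contain the correct tables. The ECG and laboratory sections do not mention treatment groups in their summary sentences either; for them too, the split by arm comes from the protocol.

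Most of this stands. A reader might infer that blood pressure, pulse, weight and BMI will get no by-arm table. The documents do not support that: the protocol requires one, and the shells have not been seen. What remains is that the SAP section meant to implement the requirement names the wrong parameters.

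A reader might also infer that postural data would explain the earlier dizziness. Neither document links the two. The protocol reports no notable treatment-related vital-sign changes at 40 mg in the two earlier patient studies, and none related to dose or treatment in Phase 1, where multiple doses went up to 200 mg daily in healthy men.

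Nor does it follow that a postural or weight effect could be neither shown nor excluded. The readings are collected, values beyond the 16.5.1 limits are flagged (including weight changes of 7% or more), and SAP Appendix 1 orders listings by randomised treatment.

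Finally, the protocol does not ask for a derived postural summary, so adding one can be called a preference. That is fair as to obligation. But both positions are measured at every visit and the SAP itself sets postural thresholds, so leaving the result in a mixed flag wastes data already in hand.

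**Conclusion.** The point holds in two parts.

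First, SAP 16.5 contains a wording error. It specifies no table for the ten measures it lists and so does not implement Protocol 13.2.11. This is a drafting correction. It is not evidence that a safety analysis has been dropped, and the shells could show that the intended tables already exist.

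Second, and independently of that wording, no by-arm summary of the standing-minus-supine difference in systolic pressure, diastolic pressure or pulse is planned in either document. This part stands on the SAP text even if the first is accepted as an obvious slip. It would change only if the unseen shells include such a table.

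The absence of formal testing between arms is not part of the point: SAP 16 applies that rule to safety data generally.

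**What to change.** In SAP 16.5:

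- Replace the reference to ECG parameters with vital signs parameters, weight and BMI, and state that summaries are by treatment group and visit.
- Add the standing-minus-supine difference in systolic pressure, diastolic pressure and pulse as derived parameters, summarised as value and change from baseline by treatment group and visit.
- Report, by arm, the number of patients who meet the existing postural criteria in 16.5.1, counted apart from the absolute-level and change criteria. The postural criterion for pulse is printed there in mmHg although the variable is in bpm; that unit should be reconciled before the count is programmed.

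Check the shells against the corrected text. The cost is one corrected sentence, three derived parameters and a few extra table rows. The data, visit schedule and thresholds are unchanged.

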**16.5.1. VITAL SIGNS ABNORMAL CRITERIA**

Abnormal quantitative vital signs measurements will be identified in accordance with the following predefined abnormal criteria:

Variable	Unit	Low	High
SBP	mmHg	$\leq 90$ mmHg OR change from baseline $\leq -20$ mmHg OR difference between supine and standing (standing – supine) $\leq -20$ mmHg	$\geq 160$ mmHg OR change from baseline $\geq 20$ mmHg OR difference between supine and standing (standing – supine) $\geq 20$ mmHg
DBP	mmHg	$\leq 50$ mmHg OR change from $\leq -10$ mmHg OR difference between supine and standing (standing – supine) $\leq -10$ mmHg	$\geq 100$ mmHg OR change from baseline $\geq 10$ mmHg OR difference between supine and standing (standing – supine) $\geq 10$ mmHg
Pulse rate	Bpm	$\leq 50$ bpm OR change from baseline $\leq -15$ bpm OR difference between supine and standing (standing – supine) $\leq -15$ mmHg	$\geq 120$ bpm OR change from baseline $\geq 15$ bpm OR difference between supine and standing (standing – supine) $\geq 15$ mmHg
Body temperature	°C	NA	$\geq 38.3$ °C OR change from baseline $\geq 1.1$ °C
Weight	Kg	percentage change from baseline $\leq -7.0$ %	percentage change from baseline $\geq 7.0$ %

Results which meet the above criteria will be flagged in the listing.

Document: C:\Users\q718413\Documents\NEP-MDD-201\_SAP\_v1.0\_Final\_06Dec2018.docx  
 Author: [name]  
 Version Number: 1.0  
 Version Date: 06Dec2018

Template No: CS\_TP\_BS016 Revision 4  
 Effective Date: 01Apr2016  
 Reference: CS\_WI\_BS005

Copyright © 2009, 2010, 2012, 2016 Quintiles Transnational Corp. All rights reserved.  
 The contents of this document are confidential and proprietary to Quintiles Transnational Corp. Unauthorized use, disclosure or reproduction is strictly prohibited.

## 16.6. SUICIDE IDEATION/SUICIDALITY

The assessment of suicidality is based on changes from baseline in the incidence rates of suicidal behavior and suicidal ideation as measured by the Columbia Suicide Severity Rating (C-SSRS). The post-baseline C-SSRS assesses the occurrence of suicidal behavior and suicidal ideation since the last visit. The occurrence of suicidal behavior and suicidal ideation are determined as follows.

- Suicidal behavior: having answered “yes” to at least one of the following four suicidal behavior items (Items 12, 14, 15, and 16 — actual attempt, interrupted attempt, aborted attempt, and preparatory acts or behavior, respectively) at any post-baseline evaluation;
- Suicidal ideation: having answered “yes” to at least one of the following two suicidal ideation items (Items 1 and 2—wish to be dead and non-specific active suicidal thoughts, respectively).

The number and percentage of patients who indicate suicidal behavior or suicidal ideation at any post-baseline visit will be summarized.

The number of discrete events of suicidal behavior, possible suicidal behavior, and non-suicidal self-injurious behavior will be captured in the Self-Harm Supplement Form (SHSF). The number of events will also be summarized at each visit. The details of each episode are captured on the Self-Harm Follow-up Form (SHFU). The information captured in the SHFU will be listed.

